At the Children’s Hospital at Montefiore (CHAM), the macrolide azithromycin is currently being used by some practitioners for its presumed anti-inflammatory effects in patients with acute asthma exacerbations. In 2010, 14% of 895 pediatric patients with a primary diagnosis of asthma received azithromycin during their inpatient stay. (Data obtained from a Clinical Looking Glass preliminary search). The length of stay of patients who received azithromycin was longer (mean: 4.5 days, median 3.8 days) than those who did not receive azithromycin (mean: 3.2 days, median 2 days) which may suggest that the current practice includes administering azithromycin to more severe asthma patients or patients refractory to standard treatments. A similar search of patients admitted with a primary diagnosis of asthma from 2008-2010 and transferred at any time to a pediatric intensive care bed, revealed that even more received azithromycin – over 30%. However, the length of stay for the critical care patients was unchanged whether they received azithromycin or not (both groups had a mean: 5.0 days, and median: 4.0 days). Although currently 14-30% of children admitted with acute asthma to CHAM receive azithromycin, there is currently no evidence on the efficacy of this treatment practice.

We propose to conduct the first double-blind, randomized, placebo-controlled trial to determine whether azithromycin will effect inpatient length of stay in children with acute asthma exacerbations.

OBJECTIVES

Primary Objective:

To conduct a double-blind, randomized, placebo-controlled trial to determine the clinical efficacy of azithromycin treatment in hospitalized children with acute asthma exacerbations, as measured by length of stay.

Secondary Objectives in a Subset of Patients – “Mechanism Subset Study”:

1. To quantify the relative prevalence of atypical infection in the inpatient pediatric asthma population.
2. To determine if atypical infection with *Mycoplasma pneumoniae* or *Chlamydia pneumoniae* is associated with treatment effect, if found.
3. To determine immunomodulatory effects of azithromycin in children hospitalized with acute asthma exacerbations, as measured by neutrophil counts, eosinophil counts, and interleukin-8.

Hypothesis:

Azithromycin treatment will decrease length of stay in children with persistent asthma hospitalized with acute asthma exacerbation.

OUTCOME MEASURES

Primary Outcome:

Length of Stay

Secondary Outcomes:

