4. Diagnosis of infection requiring antibiotics during the 3-day course of azithromycin/placebo. (However, if the diagnosis of infection and initiation of antibiotics is after the

completion of the 3-day course of azithromycin/placebo, the antibiotic will be recorded and reported. Patients given antibiotics after the completion of the 3-day course of study drug will not be withdrawn from the study and their outcomes will be included in analysis.)

Safety Exit Criteria: Worsening of clinical status requiring invasive or non-invasive ventilatory support

Study Design

This is a double-blind, randomized, placebo-controlled trial. Patients between the ages of 4-12 years of age admitted to the Children's Hospital at Montefiore (CHAM) with an admission diagnosis of asthma exacerbation, as determined by the admitting physician, will be assessed for eligibility within 12 hours of admission by study personnel. Patients may be enrolled in the pediatric emergency room, pediatric inpatient units, or pediatric intensive care unit.

Potential study patients will be identified by the pediatric emergency room staff, pediatric housestaff who will page the research pager upon admission. In addition, attending physicians in the emergency room, pediatric units, and pediatric intensive care unit can refer patients by paging the research paper. Study personnel will review with primary care team any studies (including chest x-ray) that may alter the decision to start antibiotics prior to enrollment in the study. A member of the medical team caring for the patient will approach the parent/guardian and inquire if study personnel can discuss the study with him/her. If a parent/guardian is not available, the research personnel will return when one is available. If the parent/guardian agrees, study personnel will approach him/her and complete a standardized interview to determine if the patient meets eligibility requirements (see Eligibility Questionnaire). If eligibility requirements are met, the research personnel will obtain informed consent from the parent/guardian and assent from the child (if applicable) for participation in the study. If a female patient has achieved menarche, a pregnancy test will be administered with the consent of the parent/guardian and assent of the patient. Pregnant patients will be excluded from the study.

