The research personnel will then conduct a standardized interview to obtain baseline demographic, clinical, and contact information from the parent/guardian (see Enrollment Questionnaire).

The enrolled patient will then be randomized by the Pharmacy Investigational Drug Services. Patients will either receive azithromycin suspension or indistinguishable placebo suspension once daily for three days at a dose of 10 mg/kg/dose with a maximum dose of 500 mg/dose. All research personnel, medical staff, patients, and parents/guardians will be blinded to the composition of suspension prepared in the research pharmacy. If the patient is discharged before the third dose of medication is administered, the pharmacy will provide any remaining suspension doses to be completed by patient as an outpatient.

The selection of the intervention dose of azithromycin (once daily dosing of 10 mg/kg/dose with a maximum dose of 500 mg) was made for several reasons. This dosing is shorter and more convenient to administer than the more commonly used 5 day course with 10 mg/kg/day for one day and 5 mg/kg/day for subsequent days. Since the average length of stay for patients 4-12 years old with asthma is 3 days, it is more likely that patients will complete this dosing during hospitalization. This dosing is currently recommended for other infectious indications including otitis media in penicillin allergic patients. In addition, this dosing is consistent with an open trial registered at clinicaltrials.gov in Denmark studying azithromycin treatment in children 1-3 years of age with recurrent asthma (planned enrollment November 2010 until November 2014).

At the time of enrollment, the patient will have an asthma severity score performed by research personnel via the Pediatric Asthma Severity Score (PASS), which has been validated in children 1-18 years old.^{37,38} The score will be conducted within 30 minutes prior a scheduled beta-agonist treatment or at any time if patient is on continuous albuterol. This score will be used to determine severity of the patient's asthma exacerbation at the time of enrollment.

Pediatric Asthma Severity Scoring (PASS)

Signs	0	1	2
Wheezing (= expiratory sounds heard auscultation)	None/mild	Moderate	Severe or absent due to poor air entry
Respiratory work (= utilization of accessory muscles or retractions)	None/mild	Moderate	Severe

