The primary outcome measure is hospital length of stay (LOS). Preliminary data obtained from a Clinical Looking Glass search reveals that in 2011, there were 410 children between the ages of 4-12 years admitted to CHAM with a primary diagnosis of asthma. During their admission, 237 patients received inhaled steroids, a marker of a persistent asthma diagnosis. Using this data, the mean length of stay was 3.0 days, median 2.5 days, and standard deviation 1.6. The distribution approximated normal distribution in this group. A clinically significant difference in length of stay would be 16 hours or 0.67 days (equivalent to 0.4 standard deviations).

Data analysis will be conducted with the assistance of a statistician. LOS between the two groups will be compared using independent samples t-test, if the data is normally distributed. If the data is not normally distributed, log transformation will be attempted and if the results of the transformation yield normal distribution for both groups, then t-test will be used for the logged values and reported as a geometric mean. If log transformation is not successful in yielding normal distribution, non-parametric Mann-Whitney U test will be used to report median and interquartile ranges. All tests will be two-tailed with an $\alpha = 0.05$ to denote clinical significance.

In order determine the number of patients needed to enroll to detect a 16 hour (0.67 day) difference in length of stay with a power of 80%, PASS software was utilized, with the assistance of a statistician, to model various types of adjustments for non-parametric distribution –normal distribution adjustment, uniform distribution adjustment, and logistic distribution adjustment. For each of these adjustments, the number of patients required for enrollment per

group ranged from 83 to 96 patients. Using the largest number, 96, and assuming a 10% attrition rate for parent/guardian preference, attending preference, or safety exit criteria, the sample size will need to be 107 patients in each group. We anticipate it will take approximately 15-18 months to enroll this number of patients.

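### The primary length-of-stay test ignores whether a child is in intensive care at entry, and so gives up precision that a pre-specified covariate would recover at almost no cost

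*Combined protocol and SAP*

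**What the plan says.** Under Methods, Study Design: "Patients may be enrolled in the pediatric emergency room, pediatric inpatient units, or pediatric intensive care unit". The same section leaves allocation to the pharmacy: "The enrolled patient will then be randomized by the Pharmacy Investigational Drug Services". No stratification factor, block scheme or sequence method is given anywhere.

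Under Statistical Analysis, LOS is compared by an independent-samples t-test on the raw or log scale, or by Mann-Whitney if neither scale looks normal. No covariate enters any branch. The planning sample is the 2011 admissions aged 4-12 who received inhaled steroids: "the mean length of stay was 3.0 days, median 2.5 days, and standard deviation 1.6". The target is "A clinically significant difference in length of stay would be 16 hours or 0.67 days (equivalent to 0.4 standard deviations").

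A later paragraph of that section provides for multivariable adjustment if characteristics turn out unbalanced. It names no variable and sets no threshold.

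The Background section on azithromycin use at the site reports LOS for asthma patients "transferred at any time to a pediatric intensive care bed" in 2008-2010: "both groups had a mean: 5.0 days, and median: 4.0 days", whether or not azithromycin was given. For all 2010 asthma admissions it reports: "The length of stay of patients who received azithromycin was longer (mean: 4.5 days, median 3.8 days"). The corresponding figures without the drug were 3.2 and 2 days. Of all 895 patients, 14% received azithromycin.

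**The concern.** ICU use is the patient characteristic for which the site's figures point most clearly to a longer stay, and whether a child is in the ICU at entry can be recorded before allocation. An unadjusted test leaves the spread between ICU and non-ICU children in its error term. A chance difference in the ICU share of the two arms also moves the estimated effect, and nothing pre-specified takes it out again. At stake is precision in a trial sized with little margin over 80% power.

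**Working it through.** **1. The plan's sample size reproduces.** With a difference of 0.67 days, SD 1.6, two-sided alpha 0.05 and 80% power, the t-test needs 91 per group. Dividing by the relative efficiency of the rank test gives 91/(3/π) = 96 (normal), 91/1 = 91 (uniform) and 91/(π²/9) = 83 (logistic). That is the stated range of 83 to 96. Then 96/0.90 = 107 enrolled per group. Power at 96 per group is 0.82 for the t-test and 0.805 for the rank test with the normal adjustment.

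**2. The ICU gap.** No ICU versus non-ICU comparison is given, so the gap has to be inferred.
- Simple subtractions of means: 5.0 - 3.0 = 2.0 days (2011 sample); 5.0 - 3.2 = 1.8 days (2010, no azithromycin).
- The pooled 2010 mean is 0.14 × 4.5 + 0.86 × 3.2 = 3.38 days, so 5.0 - 3.38 = 1.62 days.
- Medians: 4.0 - 2.5 = 1.5 days.

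The comparison samples are not stated to exclude ICU children. If a share p of the 2010 sample were ICU users with mean 5.0, the non-ICU mean would be (3.38 - 5p)/(1 - p), which gives the gaps in the table. The same step from the 2011 mean of 3.0 gives 2.1, 2.2 and 2.5 days.

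**3. Variance explained and power.** The share p at entry is not in the documents; 5%, 10% and 20% are assumed. The variance share is p(1 - p) × gap² / 1.6². Adjusting acts like raising n to 96/(1 - share). Power uses the normal-adjusted rank test, the basis on which 96 was chosen.

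| Assumed ICU share | Gap (days) | Variance share | Equivalent n per group | Power, unadjusted | Power, adjusted |
|---|---|---|---|---|---|
| 5% | 1.70 | 5% | 101 | 80% | about 83% |
| 10% | 1.80 | 11% | 108 | 80% | about 85% |
| 20% | 2.02 | 26% | 129 | 80% | about 91% |

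With the gap fixed at 1.5 days, the same formulas give 82%, 84% and 86%; at 2.5 days, 85%, 89% and 95%.

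**4. Chance imbalance.** The 95% range of the shift is 1.96 × gap × √(2p(1 - p)/107), or ±2.4, ±3.5 and ±5.2 hours. The whole 95% random error of the LOS difference is 1.96 × 1.6 × √(2/107) = 0.429 days, or ±10.3 hours. Taking the shift out in quadrature leaves ±10.0, ±9.7 and ±8.9 hours.

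**5. Adjusting versus stratifying.** Trials of 192 evaluable children were simulated with a 2.0-day gap, ICU shares of 10%, 20% and 30%, and 6,000 runs per setting.

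| ICU share | Adjusted power, no strata | Adjusted power, strata | Type I error, unadjusted t-test, no strata | Type I error, unadjusted t-test, strata |
|---|---|---|---|---|
| 10% | 0.872 | 0.876 | 0.045 | 0.032 |
| 20% | 0.911 | 0.916 | 0.049 | 0.022 |
| 30% | 0.938 | 0.939 | 0.049 | 0.014 |

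Stratified allocation adds at most 0.005 to the power of the adjusted test.

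**The case against.** **The plan already adjusts for imbalance.** This stands in part. The fallback deals with chance imbalance, but only after the data are seen. It is tied to the interview data and literally to parent characteristics, and it offers no method for the rank branch. It gives no precision gain when the arms happen to be balanced.

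**The shift in hours is not an added error.** This stands. Nothing says that the SD of 1.6 excludes ICU children, so the ±10.3 hours appears already to contain the shift. A reader might infer that the missing stratum biases the result or leaves the trial underpowered. The documents do not support that: unstratified randomisation is valid, and the simulated type I error was close to 0.05.

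**The gap is not firm.** This also stands. A reader might infer an ICU excess of three times the target effect. On the 2010 data, 2.02/0.67 = 3.0 holds only at an assumed 20% ICU share; 5% and 10% give 2.5 and 2.7. The subtraction crosses samples that differ in years, age range and steroid restriction. The 5.0 days is for ICU use at any time, which includes transfers that would come after randomisation. The trial excludes ventilated children, whereas the ICU search states no such exclusion, so the gap may be overstated. Backing the ICU children out of the 2011 sample instead makes it larger.

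**Silence is not a decision.** The documents support only that no stratum is stated; the pharmacy may have used one.

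**The power arithmetic is approximate.** The variance formula is a linear-model result carried over to a rank test, and a gap in days does not translate directly to the log or rank scale.

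**Conclusion.** The point holds as one about precision. The primary test leaves out a baseline factor that the site's data link to a stay roughly 1.5 to 2.5 days longer, and the conditional fallback cannot be relied on to use it. Over assumed ICU shares of 5% to 20%, adjustment is worth about 2 to 10 points of power, and little at the low end. The result rests on the assumed share, on a cross-sample gap, and on ICU status at entry predicting LOS about as well as ICU use at any time.

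A reader might also conclude that stratified randomisation is the cure. The simulation says otherwise: nearly all the gain comes from the covariate, and stratifying while keeping the planned unadjusted t-test makes that test conservative. This is a change worth making, not a flaw that invalidates the design.

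**What to change.** Record level of care at the moment of randomisation as ICU or non-ICU, counting children enrolled in the emergency room as non-ICU. Two levels suffice, since the documents give no LOS for emergency-room enrolees. Pre-specify this factor in the primary analysis regardless of observed balance: as a term in the linear model for LOS or log LOS, or through a van Elteren test stratified by it if the rank branch is reached. Later ICU transfer must not be used, because it happens after randomisation.

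Optionally, the pharmacy can keep two blocked lists by the same factor. This adds little power and should be done only together with the adjusted analysis.

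The cost is one recorded field and one sentence in the analysis plan, plus a second list and a report of the child's unit at each request if stratified. No extra patients are needed.

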- At present, there are inadequate data to correspond frequencies of exacerbations with different levels of asthma severity. In general, more frequent and intense exacerbations (e.g., requiring urgent, unscheduled care, hospitalization, or ICU admission) indicate greater underlying disease severity. For treatment purposes, patients who had ≥2 exacerbations requiring oral systemic corticosteroids in the past year may be considered the same as patients who have persistent asthma, even in the absence of impairment levels consistent with persistent asthma.
- Classifying severity in patients after asthma becomes well controlled, by lowest level of treatment required to maintain control.*

Lowest level of treatment required to maintain control (See figure 4–1b for treatment steps.)	Classification of Asthma Severity			
	Intermittent	Persistent		
		Mild	Moderate	Severe
	Step 1	Step 2	Step 3 or 4	Step 5 or 6

Key: EIB, exercise-induced bronchospasm; FEV₁, forced expiratory volume in second; FVC, forced vital capacity; ICU, intensive care unit

*Notes:

- For population-based evaluations, clinical research, or characterization of a patient's overall asthma severity after control is achieved. For clinical management, the focus is on monitoring the level of control (See figure 3–5b.), not the level of severity, once treatment is established.
- See figure 3–5b for definition of asthma control.

Exclusion Criteria: Receiving albuterol every 4 hours (q4h) at the time of enrollment, concurrent bacterial infection requiring antibiotics, antibiotics received within previous 2 weeks, contraindication to azithromycin (including allergy to macrolides), chronic lung disease other than asthma (including bronchopulmonary dysplasia, cystic fibrosis, bronchiectasis), immunodeficiency (primary or acquired), chronic systemic steroid use, invasive or non-invasive mechanical ventilation required acutely as result of current asthma admission, significant cardiac co-morbidity (including hemodynamically significant cardiac disease or arrhythmia), liver disease (hepatitis), pregnancy, seizure disorder, currently on medication contraindication for use with azithromycin, and/or previous enrollment in study.

Withdrawal from study will occur for:

1. Parent/guardian preference
2. Primary attending preference
3. Worsening of clinical status requiring invasive or non-invasive ventilatory support

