Prolongation of expiration (= ratio of the length of expiration over inspiration)	Normal/mild prolongation	Moderate prolongation	Severe prolongation

Other than the administration of azithromycin suspension or placebo, the medical treatment of the enrolled patients will be at the discretion of the medical team. The current standard of care for treatment of acute asthma exacerbations in hospitalized children includes inhaled beta-agonists and systemic steroids. The medical team often continues or initiates "controller" asthma medications during the inpatient stay (ie inhaled corticosteroids, leukotriene receptor antagonists). In addition, patients with severe asthma might receive intravenous medications (ie magnesium sulfate, terbutaline, aminophylline). No medical treatments will constitute exclusion from the study. However, invasive or non-invasive mechanical ventilatory support will be part of safety exit criteria.

At 7-10 days and again between 28 and 35 days after discharge, research personnel will contact the parent/guardian of enrolled patient for a follow-up interview. This interview will include questions about recurrence of asthma symptoms, days of work/school missed, hospital readmissions, emergency room visits, pediatrician visits, subsequent steroid courses, and medication side effects.

Mechanism Subset Study: A Pilot and Feasibility Study in a Subset of Patients

After enrollment, and at the time of the PASS asthma severity scoring, research personnel will ask parents/guardians if they would also be willing to participate in a separate subset study involving blood and nasal aspirate samples. If parents/guardians consent, they will be offered compensation for their time and inconvenience (if funding is available). If the parent/guardian is interested, the research personnel will obtain a separate, additional informed consent from the parent/guardian and assent from the child for the "Mechanism Subset Study". At that time, a nasal aspirate sample will be obtained by the research personnel (who will be trained on proper technique prior to the start of study). A blood sample will be obtained as soon as possible. A second sample of both blood and nasal aspirate will be obtained on the calendar day that is 48 hours from the first sample. Two samples will allow for baseline and post-treatment samples to be compared.

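### The plan names no analysis set and implies that children withdrawn after randomisation leave the primary length-of-stay comparison; all randomised children should be analysed as assigned

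*Combined protocol and SAP*

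**What the plan says.** **Withdrawal.** The list under Methods, Population gives four reasons: parent or guardian preference; "Primary attending preference", with no criteria; clinical worsening that needs invasive or non-invasive ventilation; and "Diagnosis of infection requiring antibiotics during the 3-day course of azithromycin/placebo". The last item adds that a child who starts antibiotics after the course is complete stays in the study and is analysed. The protocol makes no such statement for children who are withdrawn. The shorter list under Ethical Considerations, Adverse Event Monitoring repeats the first three reasons and omits the antibiotic one.

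**Sample size and analysis.** Statistical Analysis takes 96 children per arm as the number needed. It raises this to 107 for 10% attrition, attributed to parent preference, attending preference or safety exit. The section specifies the tests for length of stay and an adjustment for baseline imbalance. It does not say which randomised children enter the comparison, and intention-to-treat is not mentioned anywhere.

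**Other treatment.** Study Design says "Other than the administration of azithromycin suspension or placebo, the medical treatment of the enrolled patients will be at the discretion of the medical team", and adds "No medical treatments will constitute exclusion from the study". Staff are blinded to the suspension. The Background section notes that "the macrolide azithromycin is currently being used by some practitioners for its presumed anti-inflammatory effects in patients with acute asthma exacerbations" at this hospital.

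**The concern.** Every withdrawal reason operates after randomisation, and several can depend on how the child is doing. Ventilatory support is clinical worsening by definition. An infection that needs antibiotics, or an attending's wish to change course, may also mark a sicker child. If such children are dropped, the groups compared are no longer those that randomisation created.

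Blinding does not remove the problem. Blinded staff still react to the clinical course, so a drug that works could lead to more withdrawals on placebo. The placebo arm would then lose some of its longest stays, its mean would fall, and the benefit would look smaller than it is. The loss is also largely avoidable: stopping study drug does not stop the hospital from recording when the child goes home.

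**Working it through.** **Inputs from the plan (Statistical Analysis).** Target difference 0.67 day (16 h), SD 1.6 days, two-sided alpha 0.05, power 80%, 83 to 96 per arm before attrition, 107 after.

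**1. The plan's own figures.** The two-sample t-test needs 90.5, so 91 per arm. The Mann-Whitney adjustments give:
- normal: 91 × π/3 = 95.3, so 96
- uniform: 91
- logistic: 91 × 9/π² = 82.98, so 83

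This matches the stated 83 to 96. Attrition: 96/(1 − 0.10) = 106.7, so 107. The sample size is not in dispute. The inflation restores 96 analysed per arm if the 10% supply no primary outcome.

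**2. Size of the bias.** Let a fraction w of an arm be withdrawn, and let those children stay D days longer than the children retained. The mean over the whole arm is then the retained mean plus wD, so dropping them lowers the arm's mean by wD. The shift in the between-arm difference is

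shift = (w_placebo − w_azithromycin) × D.

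The documents give neither withdrawal rates by arm nor D. As a loose stand-in for D, I use the 2010 gap under Background, Azithromycin and Asthma at CHAM: 4.5 − 3.2 = 1.3 days between recipients and non-recipients of azithromycin.

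| Withdrawn, placebo / azithromycin (assumed) | D (days) | Shift | Share of 0.67 day |
|---|---|---|---|
| 5% / 0% | 1.3 | 0.065 d = 1.6 h | 10% |
| 10% / 0% | 1.3 | 0.13 d = 3.1 h | 19% |
| 10% / 5% | 1.3 | 0.065 d = 1.6 h | 10% |
| 10% / 10% | 1.3 | 0 | 0% |
| any | 0 | 0 | 0% |

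The zero-gap row is not idle. The same Background section reports that "the length of stay for the critical care patients was unchanged whether they received azithromycin or not" (mean 5.0 days in both groups). The shift is linear in D: a 10-point difference in withdrawal with D = 2 days would give 0.20 day, or 4.8 h, but the documents supply no basis for a gap that large.

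For scale, the standard error of the difference at 96 per arm is 1.6 × √(2/96) = 0.231 day, or 5.5 h.

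**3. Power if everyone is analysed as assigned.** Noncentral t, with effective n = n × 3/π for Mann-Whitney:

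| Per arm | Mean difference (days) | Mann-Whitney | t-test |
|---|---|---|---|
| 96, withdrawn dropped, no bias | 0.67 | 80.5% | 82.3% |
| 107, full effect | 0.67 | 84.6% | 86.2% |
| 107, 10% of azithromycin arm get no benefit | 0.67 × 0.90 = 0.603 | 76.5% | 78.4% |

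A simulation of the last row (20,000 runs, normal stays, 11 of 107 azithromycin children without benefit) gave 75.9% for Mann-Whitney. With 10% of the azithromycin arm withdrawn, power stays at 80% if those children keep about 41% of the effect (Mann-Whitney) or 19% (t-test).

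**The case against.** **Exclusion is never stated.** An allowance for attrition also fits an as-assigned analysis in which some families withdraw permission to use their data. The sentence on later antibiotics says who stays in; it does not say that anyone else's stay is discarded. This is fair. A reader might infer that the plan orders the exclusion of withdrawn children, and the text does not go that far. What stands is that no analysis set is named and that both pieces of text lean towards exclusion.

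**The 1.3-day gap is a poor proxy.** The source sentence reads "The length of stay of patients who received azithromycin was longer (mean: 4.5 days, median 3.8 days) than those who did not receive azithromycin". It concerns 895 paediatric asthma admissions in 2010 and compares users with non-users, not withdrawn with retained children aged 4 to 12 with persistent asthma. The protocol says only that the gap "may suggest that the current practice includes administering azithromycin to more severe asthma patients". This stands, and the figures in hours are illustrations. The 3.1 h end also needs all the loss to fall on one arm under blinding.

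**Open-label azithromycin.** From the local use of 14-30%, a reader might infer that many placebo children will receive azithromycin and that power will collapse. If 14-30% of the placebo arm received it with full effect, Mann-Whitney power at 107 per arm would be about 73-55%. The documents do not support that reading. Those rates are from before the trial, and the higher one is from intensive-care transfers. The discretion clause sets the study suspension apart before handing the rest to the team, and the treatments then listed include no antibiotic. Staff know that an enrolled child may already be on azithromycin. Nothing shows open-label use in enrolled children, and the data forms are not in the text, so it cannot be said to go unrecorded.

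**Direction.** A reader might also fear a spurious benefit. In the scenario examined, where the drug works and more placebo children are withdrawn, the shift is towards no difference.

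**Conclusion.** The concern holds as a minor one. The most natural reading of the plan is that children withdrawn after randomisation, some for reasons tied to outcome, leave the primary length-of-stay analysis; this is an inference. The likely bias is small: 0 to about 3 h of the 16 h target, assuming loss of at most 10% confined to or greater in the placebo arm and stays 1.3 days longer in those lost. It is near zero if the arms lose equal numbers of similar children. Even the upper figure is below one standard error of the planned comparison. Confidence is medium, because the withdrawal rates, the gap in stay and the handling of withdrawn children are all unstated. The point is worth raising because the loss can be avoided at little cost.

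**What to change.** Add to Statistical Analysis that the primary comparison includes every randomised child in the assigned arm, including those withdrawn from study drug for any listed reason, with discharge time taken from the hospital record unless permission to use data is withdrawn. Distinguish stopping study drug from withdrawing permission to use data, and check that the consent wording allows discharge time to be kept (the consent pages are not in the text reviewed). Bring the two withdrawal lists into line.

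The cost is a few sentences and no added recruitment. The statistical price is some dilution, because children who stopped early count in full. If 10% of the azithromycin arm gain nothing, power falls below the 80% target, to about 76% (Mann-Whitney) or 78% (t-test). If they keep about two-fifths of the effect or more, the target is still met.

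Optionally, record any non-study macrolide with its date and report it by arm. This would help in interpreting a null result, but the point above does not depend on it.
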